to occur during the treatment with spartalizumab, onset may be delayed and irAEs may also occur after discontinuation of study treatment (Spain et al 2016, Hofmann et al 2016, Champiat et al 2016, Haanen et al 2017, Brahmer et al 2018). In addition, mAbs can be associated with infusion-related reactions some of which can be severe; these are often immediate and usually occur within minutes of the exposure to the study drug. Therefore, infusions should take place in a facility with appropriate resuscitation equipment available at the bedside and a physician readily available, and patients monitored for respective signs and symptoms. Patients who experience severe or life-threatening irAEs or infusion reactions may need to permanently discontinue spartalizumab (see [Section 6.5](#) for further guidance).

Clinical experience with spartalizumab to date suggests that it can cause irAEs. It is therefore important to be vigilant and carefully identify events that may be suggestive of potential irAEs, as their appearance may be sub-clinical (for example an asymptomatic laboratory abnormality), and early diagnosis is critical for appropriate management and possibly prevent complications. Serological, immunological and histological assessments (such as biopsy of the affected tissue) should be performed as deemed appropriate by the investigator to verify the potential immune-mediated nature of the AE and to exclude alternative diagnoses or disease progression. Following appropriate and complete evaluation, an empiric trial of corticosteroids may contribute to the identification of irAEs.

Refer also to the latest version of the spartalizumab Investigator's Brochure for additional details on clinical and preclinical safety.

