2. its relationship to the study treatment. If the event is due to lack of efficacy or progression of underlying illness (i.e. progression of the study indication) the assessment of causality will usually be 'Not suspected.' The rationale for this guidance is that the symptoms of a lack of efficacy or progression of underlying illness are not caused by the trial drug, they happen in spite of its administration and/or both lack of efficacy and progression of underlying disease can only be evaluated meaningfully by an analysis of cohorts, not on a single subject
3. its duration (start and end dates) or if the event is ongoing, an outcome of not recovered/not resolved must be reported
4. whether it constitutes a SAE (see [Section 10.1.2](#) for definition of SAE) and which seriousness criteria have been met
5. action taken regarding with study treatment. All adverse events must be treated appropriately. Treatment may include one or more of the following:
  - Dose not changed
  - Dose Reduced/increased
  - Drug interrupted/withdrawn
6. its outcome

If the event worsens the event should be reported a second time on the eCRF noting the start date when the event worsens in toxicity. For grade 3 and 4 adverse events only, if improvement to a lower grade is determined a new entry for this event should be reported on the eCRF noting the start date when the event improved from having been grade 3 or grade 4.

Conditions that were already present at the time of informed consent should be recorded in medical history of the subject.

Adverse events (including lab abnormalities that constitute AEs) should be described using a diagnosis whenever possible, rather than individual underlying signs and symptoms.

Adverse event monitoring should be continued for at least 30 days after the last dose of capmatinib or 150 days after the last dose of spartalizumab/placebo, whichever is longer. If a patient starts a post treatment anti-neoplastic therapy sooner than the 30/150 days mentioned above, then only adverse events suspected to be related to study treatment should be collected.

Once an adverse event is detected, it must be followed until its resolution or until it is judged to be permanent (e.g. continuing at the end of the study), and assessment must be made at each visit (or more frequently, if necessary) of any changes in severity, the suspected relationship to the interventions required to treat it, and the outcome.

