##### 2.1.1.2 Date of first/last administration of study treatment

The date of first (last) administration of study treatment is derived as the start (end) date when a non-zero dose of either capmatinib or spartalizumab was administered and recorded on the study treatment eCRF.

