### 2.1.1.6 On-treatment assessment/event and observation periods

For all safety analyses, the overall observation period will be divided into three mutually exclusive segments:

- ***pre-treatment period***: from day of patient's informed consent to the day before first administration of study treatment
- ***on-treatment period***: from date of first administration of study treatment to 30 days after date of last actual administration of any study treatment (including start and stop date)
- ***post-treatment period***: starting at day 31 after date of last administration of study treatment

If dates are incomplete in a way that clear assignment to pre-, on-, post-treatment period cannot be made, then the respective data will be assigned to the on-treatment period.

Safety summaries will primarily include only data from the on-treatment period. Select summaries of related adverse events and death will be produced for the combined on-treatment and post-treatment periods of study treatment (see [Section 2.8.1](#) and [Section 2.8.2](#)).

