### 2.8.1 Adverse events (AEs)

Adverse event (AE) summaries will include all AEs occurring during on-treatment period. All AEs collected in the AE eCRF page will be listed along with the information collected on those AEs e.g., AE relationship to study drug, AE outcome etc. AEs starting during the post-treatment period will be flagged in the listings.

Adverse events (AEs) will be summarized by number and percentage of subjects having at least one AE, having at least one AE in each primary system organ class (SOC) and for each preferred term (PT) using MedDRA coding. A subject with multiple occurrences of an AE will be counted only once in the respective AE category. A subject with multiple CTCAE grades for the same preferred term will be summarized under the maximum CTCAE grade recorded for the event.

AE with missing CTCAE grade will be included in the 'All grades' column of the summary tables.

In AE summaries by primary SOC and PT, the primary SOC will be presented alphabetically and the PT will be sorted within primary SOC in descending frequency. Table by either primary SOC or PT will be sorted in descending frequency.

The following adverse event summaries will be produced for all subjects:

- Overview of adverse events summarized by relationship and deaths (number and % of subjects who died, with any AE, any SAE, fatal SAEs, AEs leading to dose reduction/interruptions, AE leading to treatment discontinuation)
- AEs by SOC and PT, summarized by relationship (all AEs and AEs related to study treatment).
- SAEs summarized by relationship (all SAEs and SAEs related to study treatment) and severity.
- AEs leading to study treatment discontinuation (all AEs and AEs related to study treatment).
- AEs leading to study treatment dose reduction/interruption.

The following listings will be produced:

- All adverse events (safety set)
- All serious adverse events (safety set) (including those from the pre and post-treatment periods)
- Adverse events among subjects who were not treated (screening failure subjects)

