## 2.8.1.1 Adverse events of special interest / grouping of AEs

An adverse event of special interest (AESI) is a grouping of adverse events that are of scientific and medical concern specific to spartalizumab and/or capmatinib. These groupings are defined using MedDRA terms, SMQs (standardized MedDRA queries), HGLTs (high level group terms), HLT (high level terms) and PTs (preferred terms). Customized SMQs (Novartis MedDRA queries, NMQ) may also be used. A NMQ is a customized group of search terms which defines a medical concept for which there is no official SMQ available or the available SMQ does not completely fit the need. It may include a combination of single terms and/or an existing SMQ, narrow or broad.

For each specified AESI for each study drug, the number and percentage of subjects with at least one event of the AESI occurring during on-treatment period will be summarized for each study drug separately:

- Overview of adverse events of special interest for capmatinib
- Overview of adverse events of special interest for spartalizumab

A listing of all grouping levels down to the MedDRA preferred terms used to define each AESI will be generated.

Note: From the eCRS, only risk where “Core Safety Risk” = Y should be selected to report Adverse events of special interest in the CSR (the variable name in GPS, for “Core Safety Risk”, is SP).

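### The spartalizumab AESI rate stops 30 days after the last dose of either drug, so a late first immune event can be collected but left out of the rate when both drugs stop at about the same time

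*SAP*

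**What the plan says.** SAP 2.8.1.1 plans one overview of AESIs for capmatinib and one for spartalizumab. For both, "the number and percentage of subjects with at least one event of the AESI occurring during on-treatment period will be summarized". SAP 2.1.1.6 defines the on-treatment period as running "from date of first administration of study treatment to 30 days after date of last actual administration of any study treatment". SAP 2.1.1.2 takes the relevant date as the "start (end) date when a non-zero dose of either capmatinib or spartalizumab was administered", so in practice the later of the two drugs sets the cut-off. Protocol 12.5.2.2 also tabulates AESIs on-treatment.

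The protocol gives spartalizumab a longer risk period. Section 4.5.2 warns that "onset may be delayed and irAEs may also occur after discontinuation of study treatment". Section 10.1.1 says "Adverse event monitoring should be continued for at least 30 days after the last dose of capmatinib or 150 days after the last dose of" the antibody (or its placebo), with the later date applying. Amendment 01 kept this: Table 8-1b runs adverse event collection on the same rule, and section 9.2.1 requires the 150-day safety assessments to be complete before an exposed subject may be transferred.

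SAP 2.1.1.6 adds that "Select summaries of related adverse events and death will be produced for the combined on-treatment and post-treatment periods of study treatment", and refers to SAP 2.8.1 and 2.8.2. Section 2.8.2 does plan an all-deaths summary. Section 2.8.1 opens with "Adverse event (AE) summaries will include all AEs occurring during on-treatment period" and names no combined-period table. Adverse events that start after treatment are flagged in the listings.

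**The concern.** A spartalizumab AESI rate should cover the time in which spartalizumab could plausibly have caused the event. Here the end of the window depends on how long the other drug was taken. Take a first hepatitis 45 days after the last spartalizumab infusion. If both drugs stopped on the same day, it is collected and listed but not in the percentage. If the subject is still on capmatinib, it is in the percentage.

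The effect also runs the other way. In a subject who stays on capmatinib for a long time, an event well past day 150 still counts as a spartalizumab AESI.

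This matters because enrollment was halted for lack of tolerability of the combination, and its safety and tolerability is a stated secondary objective. The AESI percentages will be read as the immune-toxicity profile, and a listing does not supply a rate. Stopping both drugs at once is also a foreseeable path: Protocol 6.5.1 does not allow spartalizumab to continue alone, and Table 6-3 ends all study treatment for several toxicities.

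**Working it through.** The plan gives no figure for this point, so the check compares the counting window with the collection window.

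**Inputs**
- Counting ends 30 days after the last dose of either drug (SAP 2.1.1.2, 2.1.1.6, 2.8.1.1).
- Collection ends at the later of 150 days after spartalizumab and 30 days after capmatinib (Protocol 10.1.1, Table 8-1b).
- Spartalizumab is given every 28 days; capmatinib is taken continuously (Protocol 6.7.2).
- 28 subjects received the combination; 3 more, in screening at the halt, started capmatinib alone (Protocol, Study Update). That gives 28 + 3 = 31 in the safety set, which requires a dose of either drug (SAP 2.2).
- 19 subjects were still on capmatinib on 06-Sep-2021 (Protocol, Study Update).

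**Window.** Let g be the days from last spartalizumab to last capmatinib, with g at least 0. Measured from the last spartalizumab dose:
- counted to day g + 30;
- collected to day max(150, g + 30);
- collected but uncounted: max(0, 120 − g) days.

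| g (days) | Counted to day | Collected to day | Uncounted days | Share of 150 |
|---|---|---|---|---|
| 0 | 30 | 150 | 120 | 80% |
| 28 | 58 | 150 | 92 | 61% |
| 60 | 90 | 150 | 60 | 40% |
| 90 | 120 | 150 | 30 | 20% |
| 120 | 150 | 150 | 0 | 0% |
| 150 | 180 | 180 | 0 | 0% |

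Stopping both drugs partway through a 28-day cycle leaves g between 0 and about 28, so about 92 to 120 days go uncounted. The day-45 event is missed only if 45 > g + 30, that is, if g is below 15. In the last row, counting runs 30 days past day 150.

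**Weight of one missed subject.** 1/28 = 3.6 percentage points of those exposed to spartalizumab; 1/31 = 3.2 points of the safety set.

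**Subjects off all treatment on 06-Sep-2021.** 31 − 19 = 12 overall. Among the 28 exposed, the number is 28 − 19 = 9 if none of the 3 capmatinib-only subjects were among the 19, and 28 − 16 = 12 if all three were. This does not count subjects who lost follow-up time: the gaps between their last doses are not reported.

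**The case against.** The strongest reply is that the SAP does what the protocol says. Protocol 12.5.2.2 tabulates AESIs on-treatment and bases safety summaries primarily on that period. This stands: the SAP does not depart from the protocol, and replacing the window would create a departure. But the same section allows selected related-event summaries over both periods and leaves the details to the SAP, so an added table fits.

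Second, nothing disappears from the report. Late events are listed and flagged, the listing of serious events includes the post-treatment period, and all deaths are summarized. With 28 exposed subjects a reader can go through the cases. This also stands, and it limits the loss to the percentage.

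Third, a reader might infer that the rates are biased low in the subjects with most toxicity, or that 9 to 12 of the 28 are affected. The documents support neither. The measure is at least one event, so a subject who stopped because of an AESI already counts for it; only a first event of that AESI after the window is lost. The documents do not say why those 9 to 12 subjects stopped, and progression is a listed reason. Anyone ongoing at the halt was moved to capmatinib alone, which lengthens the gap and shrinks the loss.

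Fourth, the combined-period table may be in the separate table shells, which are not part of these documents. That is possible. What can be said is that SAP 2.8.1 does not carry through the reference made to it, and that SAP 2.1.1.6 names related events and deaths, not AESIs.

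**Conclusion.** The mismatch is real but modest. The planned spartalizumab AESI rate can miss first events that the trial collects because their onset may be delayed, and whether it does so depends on capmatinib dosing. The 120-day loss is a maximum that needs both last doses on the same day. After a new anti-neoplastic therapy only suspected events are collected, so not every uncounted day is fully observed. The number of missed events could be zero and cannot be derived from the documents. The conclusion rests on reading the last study-treatment date as the later of the two drugs, and on capmatinib never stopping before spartalizumab. It supports a low-cost addition to the SAP. It does not show that the rates are materially wrong or that the SAP contradicts the protocol.

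**What to change.** - Keep the on-treatment AESI overviews as planned. A replacement window would remove events after day 150 that are now counted in subjects continuing capmatinib.
- Add to SAP 2.8.1.1 a table of spartalizumab AESIs from first spartalizumab dose to 150 days after the last one, regardless of capmatinib dosing, with the 28 exposed subjects as denominator.
- Add to SAP 2.8.1 the summary of related adverse events and related serious events over the combined on- and post-treatment periods, so that the reference from 2.1.1.6 leads to a specified output.
- Record the added AESI table in SAP section 4, which now reads as not applicable.
- Footnote the new tables to say that only suspected events are available after a new anti-neoplastic therapy.

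The data are already collected, so the cost is SAP wording and one or two extra table programs. The 150-day rates may come out slightly higher than the on-treatment ones, and the two tables need clear labels so that they are not confused.

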## 2.8.2 Deaths

Separate summaries for on-treatment deaths and all deaths (including post-treatment deaths) will be produced for all subjects by SOC and PT.

All deaths will be listed for the safety set, post treatment deaths will be flagged. A separate listing of deaths will be provided for screening failure subjects.

## 2.8.3 Laboratory data

The summaries will include all assessments (including unplanned assessment) available for the lab parameter collected no later than 30 days after the last study treatment administration date (see [Section 2.1.1.6](#)). Details on derivations are provided in [Section 5.3](#).

The following summaries will be produced for hematology and biochemistry laboratory data (by laboratory parameter and treatment):

- Shift tables using CTC grades to compare baseline to the worst on-treatment value.
- For laboratory tests where CTC grades are not defined, shift tables using the low/normal/high/(low and high) classification to compare baseline to the worst on-treatment value.

The following listings will be produced for the laboratory data:

- Listing of all CTC grade 3 or 4 laboratory toxicities

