## 10.2      Additional Safety Monitoring

### 10.2.1      Adverse events of special interest

Adverse events of special interest (AESI) are defined as events (serious or non-serious) which are ones of scientific and medical concern specific to the sponsor's product or program, for which ongoing monitoring and rapid communication by the investigator to the sponsor may be appropriate. Such events may require further investigation in order to characterize and understand them.

Adverse events of special interest are defined on the basis of an ongoing review of the safety data. AESIs are discussed in detail in the latest capmatinib and spartalizumab Investigator's Brochure.

Adverse events of special interest to be monitored for capmatinib include:

- Hepatotoxicity,
- Nausea/Vomiting,
- Peripheral oedema,
- Renal dysfunction,
- ILD/pneumonitis,
- Central nervous system toxicity,

- Increased amylase/lipase,
- Phototoxicity,
- Teratogenicity

Adverse events of special interest to be monitored for spartalizumab include:

- Endocrinopathies (i.e. hypothyroidism, hyperthyroidism, diabetes, hypophysitis, hypopituitarism, adrenal insufficiency)
- Pneumonitis
- Colitis
- Hepatitis
- Nephritis
- Skin reactions
- Other immune-mediated events
- Infusion reactions

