## **Clinical laboratory evaluations**

All laboratory data will be summarized by subject and visit/time.

Grading of laboratory values will be assigned programmatically as per NCI Common Terminology Criteria for Adverse Events (CTCAE) version 5.0. The calculation of CTCAE grades will be based on the observed laboratory values only, clinical assessments will not be taken into account.

CTCAE Grade 0 will be assigned for all non-missing values not graded as 1 or higher. Grade 5 will not be used.

For laboratory tests where grades are not defined by CTCAE v5.0,

- Shift tables using low/normal/high (low and high) classification to compare baseline to the worst on-treatment value.

The following summaries will be generated separately for hematology and biochemistry tests:

- Listing of all laboratory data with values flagged to show the corresponding CTCAE v5.0 grades if applicable and the classifications relative to the laboratory normal ranges.

For laboratory tests where grades are defined by CTCAE v5.0

- Worst post-baseline CTCAE grade (regardless of the baseline status). Each subject will be counted only once for the worst grade observed post-baseline.
- Shift tables using CTCAE v5.0 grades to compare baseline to the worst on-treatment post-baseline value.

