## 5.3 Laboratory parameters derivations

### 5.3.1 CTC grading for laboratory parameters

Grade categorization of lab values will be assigned programmatically as per NCI Common Terminology Criteria for Adverse Events (CTCAE) version 5.0. The calculation of laboratory CTC grades will be based on the observed laboratory values only, clinical assessments will not be taken into account. The criteria to assign CTC grades are given in Novartis internal criteria for CTC grading of laboratory parameters (see [Table 5-3](#)). The latest available version of the document based on the underlying CTCAE version 5.0 at the time of analysis will be used.

For laboratory tests where grades are not defined by CTCAE v5.0, results will be graded by the low/normal/high classifications based on laboratory normal ranges.

A severity grade of 0 will be assigned for all non-missing lab values not graded as 1 or higher. Grade 5 is not applicable. For laboratory tests that are graded for both low and high values, summaries will be done separately and labeled by direction, e.g., sodium will be summarized as hyponatremia and hypernatremia.

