Calcium (corrected) (Hypercalcemia)	mmol/L	CACALC	2.2 - 2.6 mmol/L or 9 - 10.5 mg/dL (0.2495 x mg/dL = mmol/L)	≤ ULN	> ULN - 11.5 mg/dL > ULN - 2.9 mmol/L	> 11.5 - 12.5 mg/dL > 3.1 - 3.4 mmol/L	> 12.5 - 13.5 mg/dL > 3.4 mmol/L	> 13.5 mg/dL > 3.4 mmol/L
Calcium (corrected) (Hypocalcemia)	mmol/L	CACALC		≥ LLN	< LLN - 8.0 mg/dL < LLN - 2.0 mmol/L	< 8.0 - 7.0 mg/dL < 2.0 - 1.75 mmol/L	< 7.0 - 6.0 mg/dL < 1.75 - 1.5 mmol/L	< 6.0 mg/dL < 1.5 mmol/L
Magnesium  (Hypermagnesemia)	mmol/L	MG	0.62 - 0.99 mmol/L or 1.5 - 2.4 mg/dL (0.4114 x mg/dL = mmol/L)	≤ ULN	> ULN - 3.0 mg/dL > ULN - 1.23 mmol/L	-	> 3.0 - 8.0 mg/dL > 1.23 - 3.3 mmol/L	> 8.0 mg/dL > 3.3 mmol/L
Magnesium  (Hypomagnesemia)	mmol/L	MG		≥ LLN	< LLN - 1.2 mg/dL < LLN - 0.5 mmol/L	< 1.2 - 0.9 mg/dL < 0.5 - 0.4 mmol/L	< 0.9 - 0.7 mg/dL < 0.4 - 0.3 mmol/L	< 0.7 mg/dL < 0.3 mmol/L
Glucose (Hypoglycemia)	mmol/L	GLUCSN/ GLUCSF		≥ LLN	< LLN - 55 mg/dL < LLN - 3.0 mmol/L	< 55 - 40 mg/dL < 3.0 - 2.2 mmol/L	< 40 - 30 mg/dL < 2.2 - 1.7 mmol/L	< 30 mg/dL < 1.7 mmol/L
Potassium (Hyperkalemia)	mmol/L	K	3.5 - 5.0 mmol/L (0.2558 x mg/dL = mEq/L = mmol/L)	≤ ULN	> ULN - 5.5 mmol/L	> 5.5 - 6.0 mmol/L	> 6.0 - 7.0 mmol/L	> 7.0 mmol/L
Potassium (Hypokalemia)	mmol/L	K		≥ LLN	< LLN - 3.0 mmol/L	-	< 3.0 - 2.5 mmol/L	< 2.5 mmol/L
Sodium (Hypernatremia)	mmol/L	SODIUM	136 - 145 mmol/L (0.435 x mg/dL = mEq/L = mmol/L)	≤ ULN	> ULN - 150 mmol/L	> 150 - 155 mmol/L	> 155 - 160 mmol/L	> 160 mmol/L
Sodium (Hyponatremia)	mmol/L	SODIUM		≥ LLN	< LLN - 130 mmol/L	-	< 130 - 120 mmol/L	< 120 mmol/L
Coagulation								
INR ↑	1	INR	0.8 - 1.2	≤ ULN	> ULN - 1.5 x ULN	> 1.5 - 2.5 x ULN	> 2.5 x ULN	-
Activated partial thromboplastin time ↑	sec	APTT	25 - 35 sec	≤ ULN	> ULN - 1.5 x ULN	> 1.5 - 2.5 x ULN	> 2.5 x ULN	-

ULN = Upper Limit of Normal range; LLN = Lower Limit of Normal range

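### The SAP grades glucose for low values only and bars it from the low/normal/high shift table, so no laboratory output it defines shows high glucose, although diabetes is a spartalizumab event of special interest

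*SAP*

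**What the plan says.** **Grading.** SAP Table 5-3 has one glucose row, "Glucose (Hypoglycemia". Grade 0 is at or above the lower limit of normal (LLN), Grade 1 is "< LLN - 55 mg/dL < LLN - 3.0 mmol/L", and Grades 2 to 4 are lower still. Calcium, magnesium, potassium and sodium each have a high row and a low row in the same table.

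**Default.** SAP 5.3.1: "A severity grade of 0 will be assigned for all non-missing lab values not graded as 1 or higher".

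**Shift tables.** SAP 2.8.3 plans shift tables by CTC grade. It adds a second kind with this scope: "For laboratory tests where CTC grades are not defined, shift tables using the low/normal/high/(low and high) classification". SAP 5.3.1 has the same limit: "For laboratory tests where grades are not defined by CTCAE v5.0, results will be graded by the low/normal/high classifications based on laboratory normal ranges". On direction it says: "For laboratory tests that are graded for both low and high values, summaries will be done separately and labeled by direction".

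**Listings.** The only laboratory listing in SAP 2.8.3 is of Grade 3 or 4 toxicities. Protocol 12.5.2.2 planned more: "Listing of all laboratory data with values flagged to show the corresponding CTCAE v5.0 grades", with each value also classified against the normal range. SAP Section 4 reports no change from the protocol analyses.

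**Why glucose matters here.** Protocol 10.2.1 names this group among the spartalizumab events of special interest: "Endocrinopathies (i.e. hypothyroidism, hyperthyroidism, diabetes, hypophysitis, hypopituitarism, adrenal insufficiency". Glucose is in the chemistry panel (protocol Table 8-5).

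**The concern.** Changes in laboratory values are a named safety endpoint (protocol Table 2-1, SAP Table 1-1). Protocol 4.5.2 warns that immune-related events can be sub-clinical and may show only as a laboratory abnormality without symptoms. Protocol Table 6-3 has an autoimmune-diabetes entry that works from graded hyperglycemia. So the protocol watches for high glucose, while the SAP's laboratory rules can tabulate only low glucose.

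A laboratory table or listing exists partly to show a change whether or not the site called it an adverse event. For high glucose that independent view is missing. Enrollment was halted because the combination was poorly tolerated, and only 28 subjects received it, so one or two cases could matter to the safety description.

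**Working it through.** No arithmetic applies. The check follows one value through the SAP rules and compares it with two other chemistry tests. The three values are assumptions chosen for illustration; baseline is normal in each case.

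**Glucose 15 mmol/L on treatment**

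1. Table 5-3: 15 mmol/L is above LLN, so no grade of 1 or more is met in the hypoglycemia row. There is no other glucose row.
2. SAP 5.3.1 default: Grade 0.
3. CTC shift table: baseline Grade 0, worst value Grade 0. This is the same cell as a subject whose glucose never left the normal range.
4. Low/normal/high shift table: not produced, because glucose is a test with CTC grades. The rule is set by test, not by direction.
5. Direction rule: it covers tests graded both ways, which glucose in Table 5-3 is not.
6. SAP listing: Grade 0 is not Grade 3 or 4, so the value is not listed.

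Step 1 has no upper limit, so the result is the same for every glucose value above ULN.

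**Comparison**

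| Test (assumed value) | Rows in Table 5-3 | CTC shift | Low/normal/high shift | SAP listing |
|---|---|---|---|---|
| Potassium, 6.5 mmol/L | High and low | Grade 0 to Grade 3 | Not needed | Yes |
| LDH, above ULN | None | Not produced | Normal to high | No |
| Glucose, 15 mmol/L | Low only | Grade 0 to Grade 0 | Not produced | No |

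Potassium is covered because both directions are graded. LDH is in the chemistry panel with no row in Table 5-3, so it is covered by the fallback. High glucose falls between the two rules.

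**Protocol against SAP.** The shift rule itself is not a departure: protocol 12.5.2.2 also sets it by test. The listing is the difference. The protocol's listing of all values, classified against the normal range, would have shown the glucose value as high. With that listing cut to Grade 3 or 4, the gap in the shift table becomes a gap in every laboratory output the SAP defines.

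**The case against.** **Important cases are caught elsewhere.** This is the strongest objection, and it largely stands. The endpoint definition requires any clinically significant laboratory abnormality to be captured as an AE. Protocol 8.4.5 and 10.1.1 require AE recording when a value is clinically significant, causes symptoms or needs therapy. Such an event enters the AE tables and the listing of all AEs (SAP 2.8.1). It may also enter the special-interest overview, subject to the core-risk filter in SAP 2.8.1.1, and its treatment would enter the concomitant-medication summary. A reader might infer that severe hyperglycemia could vanish from the study report. The documents do not support that. What is lost is the view that does not pass through the site's judgment, mainly of rises not judged clinically significant. Some of these will be post-meal values, since non-fasting samples are allowed after baseline.

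**The table may have lost a row.** The paired tests print their normal range on the high row and leave the low row blank; the glucose row has no range either. A missing hyperglycemia row is possible, but nothing in the text shows one, and the four neighbouring pairs are intact. SAP 5.3.1 also allows a later version of the internal grading criteria, but does not say that it would add high glucose.

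**The output shells are a separate document.** This stands as a limit. SAP 2.1 says the final report will contain all outputs planned there, and they are not available. The conclusion therefore covers only outputs that the SAP defines. A programmer might also read the shift rule by direction, but the text says tests.

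**The study is halted and descriptive.** True, and no efficacy result changes. Safety and tolerability are nevertheless among the objectives still to be reported.

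**Conclusion.** The gap holds on the text: any glucose above ULN is Grade 0, and no laboratory summary or listing defined in the SAP shows it as high. It is a gap in laboratory reporting only. AE reporting, patient management, ORR, DCR and PFS are not affected.

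The number affected is not given. It cannot exceed the 31 treated subjects, of whom 28 received spartalizumab; the special-interest argument applies to those 28.

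The conclusion assumes that Table 5-3 has no hyperglycemia row, which can be checked against the source PDF, and that the shift rule is applied by test, as written. The documents do not say why high glucose is ungraded. If that was deliberate, a display against the normal range is still needed. The removal of the protocol listing affects all tests and should have been declared in SAP Section 4; high glucose is where it leaves no laboratory display.

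**What to change.** 1. In SAP 2.8.3 and 5.3.1, extend the fallback rule to laboratory tests, *or directions of a test*, that have no CTC grade. Glucose then gets a low/normal/high shift table beside its hypoglycemia grades.
2. Restore the protocol 12.5.2.2 listing of all laboratory data, flagged by grade and against the normal range. Alternatively, declare its removal in SAP Section 4 and list all post-baseline glucose values above ULN with the baseline value, whatever the baseline status, and with fasting status where recorded. Subjects already high at baseline must be included, because controlled type I diabetes is permitted at entry (protocol 5.2) and worsening in them would otherwise be missed.

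Both parts are needed. A shift to high does not separate a slight rise from a large one; the listing shows the values.

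**Cost.** A few words in two SAP sections, added table rows and one listing, from data already collected. The general wording also brings in the ungraded direction of other tests, such as high platelets or low ALT, which adds rows of little interest. Some listed glucose values will be non-fasting and need to be read with that in mind.
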